Research Protocol

Date: Jan 10th, 2018

Title: Survival of Endocrowns Made from Different Ceramics

NCT number: NCT03542019

Background: Endodontically treated teeth often lose a significant amount of tooth structure due to caries or trauma, which renders them at risk of catastrophic fractures¹. Their restoration requires a means to protect the cusps from the wedging forces of occlusion. Cuspal coverage using full metal or porcelain crowns has been traditionally used and has been demonstrated to improve their survival rate^{2,3}.

Recently, the demand for more aesthetic and conservative restorations has grown, and the introduction of CAD/CAM technology has allowed the preparation and cementation of indirect restorations at the same day. Adhesive indirect restorations have become popular and their application in dentistry has involved the restoration of endodontically treated teeth. Full and partial onlays and full coverage crowns have been used successfully to provide cuspal protection⁴. The endocrown is another form of adhesive indirect restorations that incorporates the core and cuspal coverage in one unit which is then bonded to the remaining tooth structure⁵. Endocrowns can be made from different types of ceramics. Lithium disilicate ceramic has been used extensively for this purpose due to its favourable physical properties, good aesthetics and its predictable bonding to tooth structure⁶. However, when milled from ingots, it requires an additional step of crystallization which will increase marginal gaps^{7,8}. This step is also time consuming and in a busy practice may be considered a draw back to the material.

Zirconia has become a popular option in dentistry due to its superior toughness and fracture resistance compared with other types of ceramics. When the CAD/CAM technology is used, zirconia restorations are usually milled from pre-sintered blocks which must be sintered after milling in order to achieve their maximum strength. This step is time consuming.

Hybrid ceramics are a new category of ceramics with a dual ceramic-polymer network that incorporates the benefits of ceramic and composite materials offering strength, flexibility, crack prevention properties and a superior abrasion behaviour⁹. Furthermore, hybrid ceramics require no additional steps following their milling from CAD/CAM blocks. They can be bonded to the tooth straight after its milling which is a favourable property in a busy dental practice.

Clinical data on the longevity of this type of restorations is scarce¹⁰. The aim of this study is to assess the short and long-term outcomes of endocrowns made from three different materials; Lithium disilicate ceramic (IPS e.max[®]), monolithic translucent zirconia and a hybrid ceramic (Vita Enamic[®]).

Material and methods:

Sample size calculation:

Sample size per each group was set at 20 restorations based on similar studies investigating the outcome of different restorations on root canal treated teeth.

Inclusion criteria:

Root canal treated molars with significant loss of tooth structure and supra-gingival margins that are scheduled for cuspal-covering indirect restorations are included in this study.

Exclusion criteria:

- Teeth with extensive cracks or fractures
- Teeth with deep subgingival margins
- Non-functional teeth (no opposing dentition)
- Teeth with advanced periodontitis

Following root canal treatment, teeth will be randomly allocated into one of three groups according to the material of the endocrown they will receive; group A (n= 20): IPS e.max lithium disilicate ceramic, group B (n= 20): monolithic translucent zirconia, and group C (n= 20): Vita Enamic hybrid ceramic. Preparation of all teeth will be performed by the same operator. Impressions will be made using a conventional 2-stage putty and wash silicone impression material (**We'll choose one**) and the same dental technician will provide all the endocrowns by milling them from CAD/CAM blocks. Cementation will be done under rubber dam isolation using the recommended protocol for each material.

Clinical follow-up assessment will be made at 6 months, 1 year, 2 years and 5 years post-operatively. This will include assessment of the restoration integrity, marginal integrity and marginal discoloration, pink and white aesthetic scores and pocket probing depths.

Radiographic assessment will be made at 1 year, 2 years and 5 years post-operatively to detect the presence of restoration defects and recurrent caries.

Patient satisfaction will be assessed on a visual analogue scale (0-10)

All assessments will be done by an experienced independent clinician unaware of the material used.

Statistical analysis

Non-parametric tests will be used to discern any statistically significant difference between groups. Wilcoxon signed-rank and Mann-Whitney tests will be used for tooth integrity, marginal integrity and discoloration, PES&WES and patient's satisfaction. Non-parametric T-test will be used for radiographic parameters.

Weibull distribution will be used to predict long-term survival rates per each group.

Funding:

This research needs funding to cover the cost of a) the lab fees of fabricating 60 endocrowns and b) the resin cement systems. Please see attached sheet.

Data collection form (appendix 1):

Patient: _____
DOB: _____
Tooth: _____
Material (coded): _____
Date: _____

ID: _____
Phone no.: _____
e-mail: _____

a- Clinical examination:

Endocrown failure: Yes / No (Specify type of failure) _____

Weeks from cementation to failure: _____

Modified USPHS criteria (use Alpha, Bravo, Charlie and Delta as in the key)

Margins: _____

Anatomic form: _____

Texture: _____

Colour match: _____

BoP/ pockets: _____

b- radiographic examination:

Secondary caries (0: absent, 1: present) _____

Proximal caries in adjacent teeth (0: absent, 1: enamel, 2: dentine) _____

Excess cement (0: absent, 1: detectable, 2: gross): _____

Periapical infection: (0: absent, 1: present/ improving, 2: present/ not improving or getting worse) _____

c- Patient-reported satisfaction (use the VAS below):

Shade: _____

Shape: _____

Quality of proximal contacts
(Food impaction/ ability to floss) _____

Chewing ability _____

Overall satisfaction _____

1	2	3	4	5
 Very dissatisfied	 Dissatisfied	 Neutral	 Satisfied	 Very satisfied

References:

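### Does the lack of a limit on study teeth per patient undermine the comparison of materials or the survival estimates?

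*Combined protocol and SAP*

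**What the plan says.** Every design unit in Material and methods is a tooth or a restoration.

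- Sample size: "Sample size per each group was set at 20 restorations based on similar studies".
- Eligibility: "Root canal treated molars with significant loss of tooth structure and supra-gingival margins". The four exclusions also describe teeth.
- Allocation: "Following root canal treatment, teeth will be randomly allocated into one of three groups", with 20 in each group.

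The Funding section budgets for 60 endocrowns, which agrees with 3 × 20. The number of patients is not given.

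Under Statistical analysis, "Wilcoxon signed-rank and Mann-Whitney tests will be used for tooth integrity, marginal integrity and discoloration", and the same tests serve the aesthetic scores and patient satisfaction. For durability, "Weibull distribution will be used to predict long-term survival rates per each group". Neither statement mentions the patient as a unit, and the plan does not say what the signed-rank test pairs.

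The data collection form (appendix 1) has header fields for patient, ID, tooth and coded material. The clinical, radiographic and satisfaction sections follow beneath. The five satisfaction items are shade, shape, proximal contacts, chewing ability and "Overall satisfaction".

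**The concern.** Two molars in one mouth share a bite, hygiene and caries risk, so their outcomes may be correlated. An analysis that treats 60 restorations as 60 independent observations could then claim too much precision. The plan permits this situation and does not say how it would be handled. Wilcoxon signed-rank is a paired test, but with the pairing unstated it cannot be credited with dealing with it.

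Satisfaction raises a second worry. If a patient has two study crowns of different materials and gives one answer about chewing or general contentment, that answer could be filed under both materials. The true difference between them would then be understated. At stake would be the precision of the per-arm survival estimates and the sensitivity of part of the satisfaction comparison.

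**Working it through.** **Inputs.** From the protocol: 60 teeth, allocated 20/20/20 by tooth. Assumed, because the document gives neither: *f*, the share of the 60 teeth that come from two-tooth patients, and ICC, the within-patient correlation (0.1 to 0.5). Allocation is taken as independent between teeth. The target of 20 per group cannot be reproduced, since it rests on similar studies with no power inputs. The only check available is 3 × 20 = 60, which agrees with the budget.

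**Where the second tooth lands.** Once one tooth is allocated, 59 places remain, 19 of them in the same arm.

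- Same arm: 19/59 = 0.322.
- Different arm: 40/59 = 0.678.

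**Per-arm survival precision.** Design effect = 1 + *f* × (19/59) × ICC. The correct interval is wider than the naive one by √(design effect) − 1.

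| *f* | Design effect, ICC 0.1 | Wider by | Design effect, ICC 0.5 | Wider by |
|---|---|---|---|---|
| 0 | 1.000 | 0% | 1.000 | 0% |
| 1/3 | 1.011 | 0.5% | 1.054 | 2.6% |
| 1/2 | 1.016 | 0.8% | 1.081 | 3.9% |
| 1 | 1.032 | 1.6% | 1.161 | 7.8% |

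For scale, take 18 of 20 crowns surviving (assumed). The exact 95% interval is about 68% to 99%, some 30 percentage points wide. A 3.9% change in that width is 0.039 × 30 ≈ 1.2 points.

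**Between-arm comparisons.** Two teeth of one patient in different arms make the arm means positively correlated, which offsets the inflation within arms. The variance factor for a difference is 1 + *f* × ICC × (19/59 − 20/59) = 1 − *f* × ICC/59. At the extreme (*f* = 1, ICC = 0.5) it is 1 − 0.5/59 = 0.992. Ignoring the patient does not make the comparison anti-conservative.

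**Dilution of a whole-mouth rating.** Suppose a two-tooth patient gives the exact average of the two crowns and it is entered under both. For such teeth, the A-minus-B difference is multiplied by 1/2 + (1/2)(19/59 − 20/59) = 29/59. Over all teeth the multiplier is 1 − *f* + *f* × 29/59 = 1 − 30*f*/59. The loss is 0% at *f* = 0, 8% at 1/6, 17% at 1/3, 25% at 1/2 and 51% at 1.

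**Would restricting the comparison help?** One remedy compares these items only among patients whose study teeth all received one material. The simulation uses a true A-minus-B of 1, a patient standard deviation of 1.5 and a third arm midway between.

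| *f* | Patients enrolled | Patients kept | Root mean squared error, all teeth | Root mean squared error, restricted |
|---|---|---|---|---|
| 1/3 | 50 | 43 | 0.50 | 0.56 |
| 1/2 | 45 | 35 | 0.54 | 0.62 |
| 1 | 30 | 10 | 0.70 | 1.30 |

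The restriction removes the bias but increases the total error in every row.

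**Would a clustered variance help?** At *f* = 1/3 there are 10 two-tooth patients, and 10 × 19/59 = 3.2 have both teeth in the same arm, about one per arm. At *f* = 1/2 there are 15 × 19/59 = 4.8, or 1.6 per arm. A within-arm cluster variance cannot be estimated usefully from so few.

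**Cost of one tooth per patient.** Sixty patients would be needed instead of 50 at *f* = 1/3 (+20%), 45 at 1/2 (+33%) or 30 at 1 (+100%).

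**The case for a change.** The strongest argument for acting is timing. A blended rating cannot be repaired by picking one tooth per patient afterwards: in the same simulation set-up that gives 0.91, 0.83 and 0.49 of the true difference at *f* = 1/3, 1/2 and 1. One sentence in the inclusion criteria, written before enrolment, would remove both problems. It would also let readers see that 60 restorations are 60 independent patients.

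Part of this stands. The text does not settle the matter, and the arithmetic of dilution is right. But the dilution needs three things together: multi-tooth enrolment, a whole-mouth reading, and exact averaging of the two crowns. Shade, shape and proximal contacts belong to a particular tooth, so at most two of the five items are exposed. The tooth and material fields above them on the form point away from a whole-mouth reading. The sentence in the inclusion criteria is also not free, because it raises the number of patients to recruit. Randomising several teeth within a patient is a legitimate design.

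Clustering would weigh more if all of a patient's teeth went to one arm. The design effect would then be 1 + *f* × ICC, which at *f* = 1/2 and ICC 0.5 is 1.25, with intervals 11.8% wider. The protocol allocates teeth, not patients, so this case does not apply as written.

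**Conclusion.** The omission is real, but it is a gap that a competent analyst fills without an amendment. With one tooth per patient nothing is affected. With a third to a half of teeth from two-tooth patients and an ICC of 0.1 to 0.5, between-arm tests remain sound and per-arm survival intervals, if any are reported, should be about 0.5% to 4% wider. The dilution of 17% to 25% over that range is an upper bound for two satisfaction items, under a reading that the form does not favour.

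The form records patient and tooth, so patients as well as teeth per arm can be counted and reported from data already collected, and the chewing and overall items can be put to the patient about the named tooth. Stating what the signed-rank test pairs would only write down a choice the analyst has to make anyway. A limit of one tooth per patient is a debatable trade-off, restricting to single-material patients loses more than it gains, and a clustered variance would rest on one or two same-arm pairs per arm.

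The conclusion assumes independent tooth-level allocation, as the protocol's wording indicates. The values of *f* and ICC are assumptions, not figures from the document.

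### Loss of tooth structure, which the background ties to fracture risk, is neither balanced at allocation, recorded on the form nor adjusted for: a loss of precision and an unverifiable chance imbalance, not a systematic bias

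*Combined protocol and SAP*

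**What the plan says.** - **Background:** endodontically treated teeth often "lose a significant amount of tooth structure due to caries or trauma, which renders them at risk of catastrophic fractures".
- **Inclusion criteria:** the trial takes "Root canal treated molars with significant loss of tooth structure and supra-gingival margins" that are due for a cusp-covering restoration. No scale, lower limit or upper limit is given for the loss.
- **Allocation (Material and methods):** "teeth will be randomly allocated into one of three groups according to the material of the endocrown they will receive", as "group A (n= 20): IPS e.max lithium disilicate ceramic, group B (n= 20): monolithic translucent zirconia, and group C (n= 20): Vita Enamic hybrid ceramic". No sequence method, blocking, stratification or minimisation is described.
- **Sample size calculation:** "Sample size per each group was set at 20 restorations based on similar studies". No effect size, event rate, alpha or power is stated.
- **Follow-up:** "assessment of the restoration integrity, marginal integrity and marginal discoloration, pink and white aesthetic scores and pocket probing depths". These items describe the restoration and the gingiva, not the structure that remained at baseline.
- **Statistical analysis:** "Wilcoxon signed-rank and Mann-Whitney tests will be used for tooth integrity, marginal integrity and discoloration, PES&WES and patient's satisfaction", plus a Weibull fit in each group. No covariate is mentioned.
- **Data collection form (appendix 1):** it identifies the tooth, the coded material, failure and its timing, modified USPHS scores, radiographic findings and satisfaction. It has no baseline section and no entry for walls, ferrule or any other measure of remaining structure. Anatomic form is listed among the modified USPHS scores, and tooth integrity appears in the analysis only as an outcome.

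**The concern.** The protocol gives a reason to think that lost structure matters for fracture, and then leaves its distribution over three arms of 20 to chance. If one material happens to receive more of the heavily broken-down molars, it may look weaker on failure, integrity and margins. An opposite imbalance could hide a real difference. Because the form does not hold the baseline state, the analyst could neither report how comparable the arms were nor adjust the comparison. If the factor is prognostic, leaving it out of both allocation and analysis also gives up precision that a trial of this size can ill afford.

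**Working it through.** **Inputs from the documents.** Three arms of 20 teeth, 60 in total (Material and methods). The figure of 20 cannot be reproduced, because the sample size section gives no calculation.

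**Assumptions (the documents give no values).** The share of teeth in a worse category is 50% (30 of 60) or 30% (18 of 60). The failure risk is 25% in worse teeth against 5% in the others, with 20% against 5% as a weaker case. Material has no effect.

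**1. Chance imbalance.** With K worse teeth among 60 and exact arms of 20, the counts (a, b, c) have probability

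C(20,a) × C(20,b) × C(20,c) / C(60,K), with a + b + c = K.

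Summing this over all allocations gives:

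| Gap in worse teeth | Some pair, K = 30 | Some pair, K = 18 | One named pair, K = 30 | One named pair, K = 18 |
|---|---|---|---|---|
| at least 4 (20 points) | 50% | 44% | 27% | 23% |
| at least 5 (25 points) | 35% | 29% | 16% | 12% |
| at least 6 (30 points) | 19% | 13% | 8% | 6% |

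**2. Difference produced by a gap.** (gap / 20) × (risk in worse teeth − risk in others).

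- 25% against 5%, gap of 6: 6/20 × 0.20 = 0.06, that is 6 points or 1.2 failures in 20.
- 20% against 5%, gap of 6: 6/20 × 0.15 = 0.045, that is 4.5 points.

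For scale, with half the teeth worse the average risk in the first case is 0.5 × 0.25 + 0.5 × 0.05 = 0.15. The standard error of a two-arm difference is then √(2 × 0.15 × 0.85 / 20) = 0.113. The 6-point shift is about half a standard error (0.06 / 0.113 = 0.53).

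**3. Effect on the false-positive rate.** Simulation with K = 30, no material effect and a pairwise pooled z test at two-sided 5%. The z test is only an illustration, since the plan names no test for comparing failure.

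| Assumed risks | All randomisations | Gap of 0 or 1 | Gap of 6 or more |
|---|---|---|---|
| 25% against 5% | 5% | 4% | 8% |
| 20% against 5% | 5% | 4% | 7% |

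With Fisher's exact test and 25% against 5%, the rate is about 2% overall and just under 4% at a gap of 6 or more.

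**4. Precision.** For an outcome score with correlation ρ to remaining structure, adjustment removes a fraction ρ² of the residual variance: 9% at ρ = 0.3 and 25% at ρ = 0.5 (both assumed).

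**5. After stratification.** Within a stratum every complete block is balanced, so only the last, incomplete block can leave a gap. That gap is at most 1 tooth with blocks of 3 and at most 2 with blocks of 6. A gap of 4 or more becomes impossible.

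**The case against.** The strongest reply is that the trial is randomised. Chance imbalance is already part of the sampling error that the tests allow for, and the overall false-positive rate stays near 5%. This stands. A reader might infer that the comparison is biased towards one material; the plan does not support that. The higher error rate applies only conditionally, in trials where a large gap has occurred. Even then it is moderate, and under Fisher's test it stays below nominal for the risks of 25% against 5%.

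Three other strong readings go beyond the text:

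- **That lost structure is the main prognostic factor.** The Background sentence explains why root-treated teeth in general are at risk of fracture. It does not say that the degree of loss among molars given an endocrown predicts failure, and the title of the reference cited there concerns maxillary incisors.
- **That eligibility admits a wide range.** All teeth are molars with supra-gingival margins and significant loss, and extensive cracks or fractures and deep subgingival margins are excluded. This narrows the range by an unknown amount, because the term is unquantified.
- **That an imbalance could never be shown.** An impression is planned for every tooth. The documents do not say whether impressions or casts are kept, so it can only be said that the planned form would not show it. Likewise, the text is silent on stratification; it does not rule it out.

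It is also fair to say that unstratified randomisation is valid and that stratifying is a choice. The omission that weighs more is the missing baseline record, since recording alone would permit adjustment.

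**Conclusion.** The point holds as a cheap improvement to design and precision. Loss of tooth structure appears in the rationale and in eligibility, but not in the described allocation, on the form or in the analysis. A gap of 30 points between some pair of arms is plausible (19% or 13% of trials for 50% or 30% worse teeth), though for any one named pair it is uncommon (8% or 6%). Its consequence is a conditional false-positive rate of roughly 7% to 8% instead of 4%, together with avoidable loss of precision. The imbalance figures rest on the assumed severity mix, and the error rates also on the assumed failure risks. If remaining structure has little bearing on failure within the eligible molars, the gain from the change is correspondingly small.

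**What to change.** 1. Count the remaining coronal walls of each tooth before allocation, and add the count to the data collection form as a baseline entry.
2. Allocate from two concealed permuted-block lists (mixed blocks of 3 and 6), one for teeth with fewer and one for teeth with more remaining walls. Fix the cut-off before enrolment.
3. Prespecify this two-level factor as the only stratification or adjustment factor in the between-material comparisons. Few failures are likely, so further covariates would not be supportable.

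If only part is adopted, step 1 matters most.

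**Cost:** one chairside count, one form field and a second list. Arms will usually end at 19 to 21 instead of exactly 20; the extremes are 18 and 22, and arms fall outside 19 to 21 in about 4% of simulated trials.

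### Marginal integrity and marginal discoloration are both planned and tested, but the form has one 'Margins' grade, so the two outcomes cannot both be derived

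*Combined protocol and SAP*

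**What the plan says.** The Material and methods section sets the clinical visits: "Clinical follow-up assessment will be made at 6 months, 1 year, 2 years and 5 years post-operatively". The assessments at those visits include "marginal integrity and marginal discoloration, pink and white aesthetic scores and pocket probing depths". Integrity and discoloration of the margin are named there as two items.

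The Statistical analysis section carries both forward: "Wilcoxon signed-rank and Mann-Whitney tests will be used for tooth integrity, marginal integrity and discoloration, PES&WES and patient's satisfaction". It does not say whether the margin is to be one variable or two.

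Part a of the Data collection form (appendix 1) gives the instruction "Modified USPHS criteria (use Alpha, Bravo, Charlie and Delta as in the key" and then five blanks: 'Margins', 'Anatomic form', 'Texture', 'Colour match' and 'BoP/ pockets'. No blank is labelled marginal discoloration or staining. The key is not in the text available. That may be a loss in extraction, and it is not counted here as a fault of the plan.

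The group size was fixed by precedent: "Sample size per each group was set at 20 restorations based on similar studies".

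**The concern.** Two outcomes that are planned and tested share one field. What is not recorded separately at a visit cannot be reliably reconstructed years later, and the visits run to 5 years. With three groups of 20 teeth and four clinical visits, up to 3 × 20 × 4 = 240 margin assessments are affected at full retention.

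The margin is also a place where the plan itself expects a difference. The Background says that the crystallization step for milled lithium disilicate widens the marginal gap, and that the hybrid ceramic needs no further step after milling. A reader will therefore want a clean comparison of marginal integrity. If staining is folded into the same letter, a difference in gaps could be diluted, or a difference in staining could be reported as loss of integrity.

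**Working it through.** The plan gives no figure to reproduce, so the main check sets the planned outcomes against the form.

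**1. Outcomes against fields**

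| Planned assessment (Material and methods) | Test named (Statistical analysis) | Field on the form |
|---|---|---|
| Marginal integrity | Yes | 'Margins', if that is what it means |
| Marginal discoloration | Yes | None of its own |
| Pocket probing depth | None named | 'BoP/ pockets', shared with bleeding |

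**2. Possible meanings of 'Margins'**

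- Integrity only: integrity is derivable and discoloration is never recorded.
- Discoloration only: the reverse.
- Both combined, for example the worse of the two: Alpha means that both are sound, but any other letter leaves open which feature failed.
- A distinct meaning for each letter: two items with four grades each have 4 × 4 = 16 combinations, and one letter has 4 values. At best it could code presence or absence of each feature (2 × 2 = 4). The letters would then no longer be an ordered grade, and severity would be lost.

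Under none of these does the form yield two graded outcomes.

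**3. Size if the grade is combined: a single example**

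Assumed counts, two-level grade (Alpha or not), 20 teeth per group: in material X, 5 teeth have a gap and no stain; in material Y, 5 teeth have a stain and no gap.

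- Separate lines, each 5/20 v 0/20. Fisher two-sided: 2 × C(20,5)/C(40,5) = 2 × 15,504/658,008 = 0.047. Mann-Whitney with tie correction: z² = (39/40) × 40 × (5 × 20)²/(20 × 20 × 5 × 35) = 5.57, z = 2.36, p = 0.018 (0.019 with continuity correction).
- Combined grade: 5/20 v 5/20, p = 1.

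**4. Size if the grade is combined: a range of rates**

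Assumed: non-Alpha rates of p1 on integrity and p2 on discoloration in X, reversed in Y; features independent; n = 20 per group; two-sided alpha 0.05.

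Power for one separate item = Φ{[|p1 − p2|√n − 1.96√(2p̄(1 − p̄))]/√[p1(1 − p1) + p2(1 − p2)]}, where p̄ is the mean of p1 and p2. For 40% v 5%, p̄ = 0.225: (0.35 × 4.472 − 1.96 × 0.5906)/0.5362 = 0.76, so power is 78%.

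Rate on a worst-of-two grade = 1 − (1 − p1)(1 − p2). For 40% and 5% this is 1 − 0.60 × 0.95 = 43.0%, the same in both materials.

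| p1 v p2 | Power per separate item: formula | Mann-Whitney simulation, 4,000 runs | Combined rate in each material | Rejection on combined grade, simulated |
|---|---|---|---|---|
| 30% v 5% | 55% | about 60% | 33.5% | about 5% |
| 40% v 5% | 78% | about 82% | 43.0% | about 4% |
| 50% v 5% | 92% | about 94% | 52.5% | about 4% |

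The combined grade rejects at about the nominal error rate because the rates were chosen to be exactly opposed. If 'Margins' means one feature only, steps 3 and 4 do not apply: nothing cancels, and the loss is the missing outcome.

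**The case against.** The strongest reply is that the meaning of 'Margins' rests on a key that is not in the text available. If the key defines it as integrity only, integrity is fully derivable, nothing is pooled, and the one fault is a missing discoloration line. This stands, and it limits the consequence. It does not remove the mismatch, because a key defines what a letter means and does not add a second field. An assessor could write two letters in the blank, but nothing on the form asks for that.

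Two stronger readings are tempting. A reader might infer that neither margin outcome can be derived and that opposite weaknesses of the materials will cancel. Both need a combined grade, which the documents do not state. A reader might also infer that the hybrid is expected to stain. The Background predicts wider gaps for lithium disilicate, but it predicts staining for no material and presents the hybrid's ceramic-polymer network as an advantage. Only one half of the supposed opposition has a source.

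The illustrations are also favourable to the point. They assume exact opposition and two grade levels, whereas four levels might still separate the groups by severity. With three pairwise comparisons, a Bonferroni threshold of 0.05/3 = 0.0167 would not be met by p = 0.018 or by p = 0.047.

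On pockets, the reply largely succeeds. 'BoP/ pockets' is an open blank that could hold both a bleeding entry and millimetres, and no test is named for depth. It cannot be said that depth is lost, only that the form does not ensure that it is captured.

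**Conclusion.** The point holds in a limited form. Two margin outcomes are planned and tested, the form has one margin grade, and so at least one of them cannot be derived as a graded outcome, whatever the key says. This follows from the documents alone and needs no assumed rate.

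Masking or misattribution of differences between materials is conditional on a combined grade. Its size in the examples (p = 0.018 becoming p = 1, or power of 55% to 92% falling to about 4% to 5%) rests on assumed, exactly opposed rates and shows only what could happen.

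The survival analysis is not touched, since the form records failure and weeks to failure separately. The point is worth acting on because the correction is small and the information cannot be recovered later. The pockets entry is a lesser matter of reliable capture.

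**What to change.** 1. Replace 'Margins' on the form with two lines, 'Marginal integrity' and 'Marginal discoloration', each graded Alpha to Delta, and give each its own written criteria in the key. Without separate criteria the two lines would not solve the problem.
2. In the Statistical analysis section, name the two as separate variables and apply the planned group comparison to each.
3. Secondary: replace 'BoP/ pockets' with bleeding on probing (yes/no) and probing depth in mm. If depth is to be compared between groups, the analysis section should say so, since it names no test for it now.

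The cost is two extra form lines and one or two more outcomes to compare, which adds slightly to multiplicity. The assessor already has to assess the margin and probe the pockets, so no procedure is added. The change is best made before the 6-month visits. If some have already been graded, the plan should state what 'Margins' meant at those visits.

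### No primary outcome, visit, significance level or multiplicity rule is named and survival gets no between-group comparison, so the chance of a false material difference is several times 5%

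*Combined protocol and SAP*

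**What the plan says.** The title is "Survival of Endocrowns Made from Different Ceramics". The Background section closes with a broader purpose: "The aim of this study is to assess the short and long-term outcomes of endocrowns made from three different materials". Neither ranks one outcome above another.

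Material and methods sets the schedule: "Clinical follow-up assessment will be made at 6 months, 1 year, 2 years and 5 years post-operatively". On content it says: "This will include assessment of the restoration integrity, marginal integrity and marginal discoloration, pink and white aesthetic scores and pocket probing depths". For imaging: "Radiographic assessment will be made at 1 year, 2 years and 5 years post-operatively to detect the presence of restoration defects and recurrent caries". A satisfaction rating from patients is also planned, with no visit attached.

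Statistical analysis opens with "Non-parametric tests will be used to discern any statistically significant difference between groups". It assigns rank tests (Wilcoxon signed-rank and Mann-Whitney) to tooth integrity, the margin, discoloration, the aesthetic scores and satisfaction, and a further test to the radiographic findings. Survival appears only as a Weibull prediction made separately for each group. The section gives no significance level, primary outcome, primary visit or multiplicity adjustment.

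The data collection form adds items that neither the methods nor the analysis names, such as anatomic form, texture and colour match. It also records whether the endocrown failed and the number of weeks from cementation to failure.

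**The concern.** Two things are missing together. First, nothing says which result decides the trial. With several scores, up to four visits and no ranking, a report could rest on whichever score and visit happened to separate the materials, and a reader could not tell a planned finding from a selected one. The differing outcome lists widen that choice. Second, the question in the title has no planned comparison: three separate Weibull predictions do not test whether the materials differ in failure.

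This is distinct from how three materials should be compared within one outcome at one visit. It remains even if every outcome and visit gets a single valid three-group test. At stake is a claim that one ceramic outperforms another on a secondary score in 60 teeth, made with a false-positive risk well above the usual 5%.

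**Working it through.** **No figure to reproduce.** The only design number is 20 restorations per group. It comes without a significance level, power or effect size, and no overall error rate is stated.

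**Assumptions, none of them in the documents.** A 5% level per test, no true difference between materials, and one overall three-group test per outcome and visit.

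**Counting tests.** The documents give no count, so it is inferred.

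- The analysis section names five outcomes: tooth integrity, marginal integrity, discoloration, the aesthetic scores taken as one, and satisfaction. At four visits that is 5 × 4 = 20, with satisfaction assumed at each visit.
- The methods give two radiographic outcomes at three visits: 2 × 3 = 6.
- Total: 20 + 6 = 26, over seven outcomes. Replacing satisfaction with probing depth, which is in the methods but has no named test, also gives 26. Leaving out both gives 4 × 4 + 6 = 22.
- If the seven outcomes are compared at a single visit: 7.

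**Independent tests.** The chance of at least one false positive among m tests is 1 − 0.95^m.

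| Tests | Calculation | Chance |
|---|---|---|
| 7 | 1 − 0.95^7 | 30% |
| 22 | 1 − 0.95^22 | 68% |
| 26 | 1 − 0.95^26 | 74% |

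The chance passes 50% from 14 independent tests. The expected number of false positives among 26 is 26 × 0.05 = 1.3. At a 1% level, 26 independent tests give 1 − 0.99^26 = 23%.

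**Correlated tests.** Scores repeat on the same teeth, so independence is the upper end. Simulating 26 correlated three-group chi-square statistics (2 degrees of freedom) under no difference gave:

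| Correlation between visits / between outcomes | Chance, 26 tests |
|---|---|
| 0.7 / 0.3 | 57% |
| 0.8 / 0.5 | 45% |
| 0.9 / 0.6 | 35% |

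A separate simulation with Kruskal-Wallis tests on 20 per group gave 56% and 44% in the first two settings, and 32% at 0.9 / 0.7.

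**Sparse data.** With mostly good scores and rare radiographic events, under assumed event rates, the Kruskal-Wallis result fell from 73% to between 62% and 69% with no correlation. At 0.9 / 0.5 it rose from 40% to between 43% and 46%. Coarse scoring therefore narrows the range but does not bring it near 5%.

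**Power if failure becomes primary.** With 20 per group, a three-group chi-square test at 5% and complete follow-up:

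| Assumed 5-year failure | Expected failures | Power |
|---|---|---|
| 5% / 5% / 15% | 1 + 1 + 3 = 5 | about 16% to 17% |
| 5% / 5% / 20% | 1 + 1 + 4 = 6 | about 31% |
| 5% / 5% / 30% | 1 + 1 + 6 = 8 | about 64% |

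These failure rates are illustrative. The documents give none.

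**The case against.** The strongest reply is that the plan schedules assessments, not tests. It never says that the materials will be compared at every visit, and one of the named tests, Wilcoxon signed-rank, is a paired test, so part of the analysis may concern change within groups. That stands. It is why the single-visit count of 7 belongs beside 26, and why 26 is called inferred.

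It can also be said that the phrase "discern any statistically significant difference between groups" is ordinary wording for the purpose of a test, not a rule that one significant score wins the trial, and that the title and the Weibull model show that survival matters most. The first part is fair: no sentence says a material will be declared better on a single score. But prominence in the title does not make survival a declared primary outcome, and the Weibull model as described compares nothing.

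A reader might infer that a false difference is more likely than not. The documents do not support that. It needs an unstated 5% level, testing at every visit, and no more than moderate correlation. It fails at 0.8 / 0.5 and 0.9 / 0.6, and fails for 7 tests even under independence. Mann-Whitney compares two groups, and three unadjusted pairwise tests per outcome and visit (78 in all) gave 58% to 97% in simulation. That figure, however, also assumes testing at every visit and every pair tested without adjustment, neither of which is stated. It belongs to the separate question of how three groups are compared.

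**Conclusion.** The point holds in bounded form. The primary outcome, primary visit, significance level and multiplicity rule are absent, and the title question has no between-group comparison. This is more than missing detail, because the plan as written leaves the deciding result open.

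At an assumed 5% level with no true difference and one overall test per comparison, the chance of at least one false difference is about 35% to 74% if all visits are tested, and up to about 30% if one visit is. The lower end of the first range depends on how strong a correlation is assumed. A stricter level would lower all of these figures. The risk is several times the nominal 5%. That it exceeds one half is not shown.

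**What to change.** Replace the opening sentence of Statistical analysis with wording such as:

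> The primary outcome is endocrown failure up to 5 years, measured as time from cementation to failure and compared between the three materials with one overall three-group log-rank test at two-sided 5%. Pairwise comparisons are made only if that test is significant. All other outcomes are secondary, each with one between-group comparison at 5 years, labelled exploratory. Earlier visits, and form items not listed in the methods, are reported descriptively with intervals.

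Word the main conclusion from the primary outcome. No new data are needed, because the form already records failure and weeks to failure. The Weibull predictions can stay as description.

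There are two costs to disclose. Early and secondary differences can no longer be presented as confirmed. Power for failure is low at 20 per group, so a non-significant result must be reported with intervals and not as equivalence of the materials.

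The choice of primary outcome belongs to the investigators. If they prefer another single outcome, it must be fixed before any outcome data are seen.
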